^h Clinical laboratory tests (including serum chemistry, hematology, coagulation, and urinalysis) may also be performed at any time if clinically indicated. Coagulation laboratory tests are performed at screening only. Glomerular filtration rate will be calculated at screening only. At baseline (visit 2; week 0), visit 11 (week 8), and at the EOT visit, clinical laboratory tests will also include hemoglobin A1C. Patients must fast for at least 8 hours prior to baseline (visit 2; week 0), visit 11 (week 8), and the EOT visit (and preferably the ET visit). At screening (prior to intake of oral olanzapine, where relevant), baseline (visit 2; week 0 [prior to IMP administration]), visit 11 (week 8 [prior to IMP administration]), and at the EOT visit, clinical laboratory tests will also include prolactin. Additionally, toxicological blood test should be collected as soon as a potential PDSS event is suspected. In cases where performing toxicological blood test is not feasible due to a lack of suitable analytical facilities, a urine drug screen may be performed instead. In case visit 3 safety laboratory blood samples cannot be shipped to the central laboratory on the same day, the samples may be processed in the local clinical laboratory instead. If needed, an additional set of safety laboratory tests may be collected for that purpose. In case visit 3 occurs over the weekend and the local safety laboratory tests cannot be processed on the collection day, visit 3 safety laboratory samples will be collected up to 2 days after the visit 3 nominal date and sent to the central laboratory.

ⁱ Includes HIV, HBsAg, hepatitis C antibody, TSH, T₃, and T₄. Virology (HIV, HBsAg, and hepatitis C antibody) is only performed at screening.

^j The FSH test will only be performed for women with no menses for 12 months prior to screening in order to confirm postmenopausal status.

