¹ Clinical laboratory tests (including serum chemistry, hematology, coagulation, and urinalysis) may also be performed at any time if clinically indicated. At visit 11 (week 8), visit 14 (week 20), visit 17 (week 32), visit 20 (week 44), and at the EOT visit, clinical laboratory tests will also include hemoglobin A1C. Patients must fast for at least 8 hours prior to visit 11 (week 8) and the EOT visit (and preferably the ET visit). At visit 11 (week 8 [prior to IMP administration]), visit 14 (week 20 [prior to IMP administration]), and at the EOT visit, clinical laboratory tests will also include prolactin. Additionally, toxicological blood test should be collected as soon as a potential PDSS event is suspected. In cases where performing toxicological blood test is not feasible due to a lack of suitable analytical facilities, a urine drug screen may be performed instead.

^m Includes TSH, T₃, and T₄.

ⁿ Full physical examination will be conducted at unscheduled visits only; the rest of the visits will include an abbreviated physical examination (including weight).

^o Vital signs (blood pressure [systolic/diastolic], pulse and orthostatic changes, respiratory rate, and temperature) should be measured at each in-clinic visit pre-injection. Before blood pressure and pulse are measured, the patient must rest in a supine or semi-erect position for at least 5 minutes; measurements should be taken again after standing for approximately 2 minutes. [REDACTED]

Vital signs should also be measured in the event of an injection site

[REDACTED] pus-containing lesion (abscess, infection, or inflammation), ulceration, or necrosis.

^p Single measurements will be performed at all in-clinic visits where ECG recordings are taken.

^q Urine β -HCG (dipstick) test: a negative result must be obtained prior to administration of IMP, as applicable (if a borderline result is obtained on a urine test, a serum test should be performed and a negative result obtained prior to IMP administration).

^r CGI-I during Period 2 will be relative to the CGI-S score at the baseline visit (visit 2 in Period 1).

^s This assessment is optional and applicable in the US only for patients who sign a dedicated ICF for participation in this assessment. This assessment will be performed only after the PANSS, CGI-S, PSP, PGI-I, CGI-I, and SQLS are complete (as applicable).

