- i. The patient has taken clozapine or has received electroconvulsive therapy within the last 12 months prior to screening.
- j. The patient is currently receiving daily oral olanzapine at a dose >20 mg/day.
- k. The patient has current or a history of known hypersensitivity to olanzapine or any of the excipients of TV-44749 or the oral formulation of olanzapine.
- l. The patient has treatment-resistant schizophrenia according to medical and psychiatric history, as judged by the investigator or documented failure of 2 or more antipsychotic medications (administered at the maximum tolerated dose for at least 6 weeks each). Participants who have responded to antipsychotics only when paired with clozapine are considered treatment resistant.
- m. The patient has had a significant sedation or delirium after antipsychotic treatment according to medical and psychiatric history and as judged by the investigator or suffered from delirium due to a medical condition.
- n. [Revision 1] The patient has any medical or psychiatric condition that, in the opinion of the investigator, could jeopardize study participant's safety (including in the context of local oral olanzapine label) or would compromise the patient's ability to participate in this study.
- o. The patient has known risk factors for undiagnosed/instable arrhythmia, congenital long QT, hypokalemia, hypomagnesemia, or autonomic failure (mostly with clinically significant orthostatic hypotension).
- p. The patient has any clinically significant uncontrolled medical condition (treated or untreated).
- q. Any disorder that may interfere with absorption, metabolism, or elimination of olanzapine
- r. The patient has a non-fasting glucose level of ≥200 mg/dL at screening.
- s. The patient had a change in their diabetes treatment within 4 weeks before the first injection of the IMP.
- t. The patient has serum triglycerides levels of ≥500 mg/dL.
- u. The patient has low-density lipoprotein levels of ≥190 mg/dL.
- v. The patient has a history of ketoacidosis or hyperosmolar coma.
- w. [Revision 1] The patient has alanine aminotransferase (ALT)/serum glutamic pyruvic transaminase values $\geq2 \times$ the upper limit of normal (ULN) of the performing laboratory, and aspartate aminotransferase (AST)/serum glutamic oxaloacetic transaminase values $\geq2 \times$ ULN, and total bilirubin values $\geq1.5 \times$ ULN at screening.

Isolated parameters for exclusion are as follows:

- ALT or AST $>5 \times$ ULN

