Potassium	Hematocrit	Hemoglobin
Chloride	Erythrocytes	pH
Creatinine ^a	Platelets	Specific gravity
Glucose	Leucocytes	Microscopic tests
BUN	Neutrophils	Bacteria
Total cholesterol	Lymphocytes	Erythrocytes
LDL	Eosinophils	Leucocytes
HDL	Monocytes	Crystals
Triglycerides	Basophils	Casts
Urate	Coagulation^d	
ALT	PT	
AST	INR	
LDH		
GGT		
Alkaline phosphatase		
Creatine kinase		
Bicarbonate		
Protein		
Albumin		
Bilirubin		
Direct bilirubin		
Prolactin ^b		

^a Glomerular filtration rate (to be calculated at screening only) will be calculated based on serum creatinine levels, weight, gender, and age using the Cockcroft-Gault equation.

^b At screening (prior to intake of oral olanzapine, where relevant), baseline (visit 2; week 0 [prior to IMP administration]), visit 11 (week 8 [prior to IMP administration]), visit 14 (week 20 [prior to IMP administration]), and at the EOT visit, clinical laboratory tests will also include prolactin.

^c At baseline (visit 2; week 0), visit 11 (week 8), visit 14 (week 20), visit 17 (week 32), visit 20 (week 44), and at the EOT visit, clinical laboratory tests will also include hemoglobin A1C.

^d At screening only.

ALT=alanine aminotransferase; AST=aspartate aminotransferase; BUN=blood urea nitrogen; EOT=end-of-treatment; ET=early termination; GGT=gamma-glutamyl transpeptidase; HDL=high-density lipoprotein; IMP=investigational medicinal product; INR=international normalized ratio; LDH=lactate dehydrogenase; LDL=low-density lipoprotein; PT=prothrombin time.

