- Abbreviated physical examination, including weight
- 12-lead ECG
- Vital signs measurement
- Urine β -HCG test for women of childbearing potential
- PANSS
- CGI-S
- AIMS
- BARS
- SAS
- C-SSRS
- PSP
- SQLS
- [REDACTED]
- CDSS
- [REDACTED]
- Abdominal fat measurement (waist-to-hip ratio)
- Blood samples for plasma concentration of IMP
- Blood samples for plasma concentration of IMP at 2.5 to 3 hours postdose
- Blood samples for biomarker analysis
- Blood samples for pharmacogenetics
- Adverse events inquiry (including serious adverse event reporting and injection site related events [including pain])
- Injection site findings and pain assessment
- Inquiry regarding alcohol consumption/illicit drug use
- Cigarette use assessment
- IMP administration
- Concomitant medication inquiry

b. Procedures for Visit 3 (Day 2, Week 0)

The following procedures and assessments will be performed at visit 3:

- Clinical laboratory tests (serum chemistry, hematology, and urinalysis)
- Abbreviated physical examination
- Vital signs measurement
- Blood samples for plasma concentration of IMP
- Adverse events inquiry (including serious adverse event reporting and injection site related events [including pain])
- Injection site findings and pain assessment
- Concomitant medication inquiry

c. Procedures for Visit 4 (Day 8, Week 1), Visit 5 (Day 15, Week 2), Visit 6 (Day 22, Week 3), Visit 8 (Day 36, Week 5), Visit 9 (Day 43, Week 6), and Visit 10 (Day 50, Week 7)

The following procedures and assessments will be performed at visits 4, 5, 6, 8, 9, and 10:

- Vital signs measurement
- PANSS
- CGI-S
- AIMS
- BARS
- SAS
- C-SSRS
- Patient Global Impression-Improvement (PGI-I) (visit 5 only)
- [REDACTED]
- Blood samples for plasma concentration of IMP
- Adverse events inquiry (including serious adverse event reporting and injection site related events [including pain])
- Injection site findings and pain assessment
- Inquiry regarding alcohol consumption/illicit drug use (for outpatients only)
- Concomitant medication inquiry

d. Procedures for Visit 7 (Day 29, Week 4) and Visit 11 (Day 57, Week 8)

The following procedures and assessments will be performed at visits 7 and 11:

- Clinical laboratory tests (serum chemistry, hematology, and urinalysis)
- Thyroid test (visit 11 only)
- Randomization (visit 11 only)

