Visit 11 (week 8) assessments are included in both [Table 1](#) (Period 1) and [Table 2](#) (Period 2) for completeness; however, they need to be performed only once, prior to randomization to Period 2. They are listed only once in this appendix (under Period 1).

Note: Patients who do not meet RDQ criteria, but in the opinion of the investigator show sufficient clinical stabilization for transition to Period 2 and may benefit from continuation of participation in the study, may continue to Period 2 as inpatients for up to an additional 8 weeks. For such patients, RDQ can be assessed periodically according to investigator discretion; if RDQ criteria are not met by the end of the additional 8-week hospitalization period (week 16), then the patient will be discontinued from study treatment and will be asked to complete early termination (ET) and follow-up (FU) visits.

a. Visit 12 (Week 12), Visit 14 (Week 20), Visit 16 (Week 28), Visit 18 (Week 36), Visit 20 (Week 44), and Visit 22 (Week 52)

The following procedures and assessments will be performed at visits 12, 14, 16, 18, and 20:

- Clinical laboratory tests (serum chemistry, hematology, and urinalysis) (visits 14 and 20 only)
- Urine drug screen
- Concomitant medication inquiry
- Abbreviated physical examination, including weight
- Abdominal fat measurement (waist-to-hip ratio)
- Vital signs measurement

- Urine β -HCG test for women of childbearing potential
- PANSS
- CGI-S
- CGI-I (visits 14 and 20 only)
- AIMS (visits 14 and 20 only)
- BARS (visits 14 and 20 only)
- SAS (visits 14 and 20 only)
- C-SSRS
- PSP (visits 14 and 20 only)
- SQLS (visits 14 and 20 only)
- [REDACTED] (visits 14 and 20 only)
- CDSS
- [REDACTED]
- Blood samples for plasma concentration of IMP
- Blood samples for plasma concentration of IMP at 2.5 to 3 hours postdose
- IMP administration
- Adverse events inquiry (including serious adverse event reporting and injection site related events [including pain])
- Injection site findings and pain assessment
- Inquiry regarding alcohol consumption/illicit drug use
- Cigarette use assessment

b. Visit 13 (Week 16), Visit 15 (Week 24), Visit 17 (Week 32), Visit 19 (Week 40), and Visit 21 (Week 48)

The following procedures and assessments will be performed at visits 13, 15, 17, 19, and 21:

- Clinical laboratory tests (serum chemistry, hematology, and urinalysis) (visit 17 only)
- Urine drug screen
- Concomitant medication inquiry
- Abbreviated physical examination, including weight

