8.6. Clinical Laboratory Tests

Clinical laboratory tests (serum chemistry, hematology, urinalysis) are detailed in Table 9 of the study protocol. Central laboratory value and changes from baseline will be summarized.

Laboratory test results will be presented in standard international (SI) units. Listings will include all laboratory values (central and local laboratories).

Laboratory test results will be presented for Period 1 and for the integrated study periods.

Summary statistics for chemistry, hematology and urinalysis laboratory tests will be presented at time points detailed in the Schedule of Assessment Table 1 and Table 2 of the study protocol.

Laboratory values and changes from baseline to each scheduled visit will be summarized using descriptive statistics.

Shifts (below, within, and above the normal range) from baseline to each scheduled visit including "at any visit" assessment (as a separate visit) will be summarized using patient counts. Summaries of potentially clinically significant abnormal values will include all post-baseline values (including scheduled, unscheduled, and withdrawal visits). The incidence of potentially clinically significant abnormal values will be summarized for laboratory variables using descriptive statistics with the criteria specified in [Table 2](#) below.

Summaries will be presented for the While on treatment period (starting from the baseline visit in Period 1 to the EOT visit, including ET visit if conducted during this period). A separate summary will be presented for the Follow-Up period (any visit conducted after EOT visit and until the end of the study).

Table 2: Criteria for Potentially Clinically Significant Laboratory Values

Test	Criterion value
Serum chemistry	
Alanine aminotransferase (ALT)	$\geq 3x$ ULN
Aspartate aminotransferase (AST)	$\geq 3x$ ULN
Alkaline phosphatase	$\geq 3x$ ULN
Lactate dehydrogenase (LDH)	$\geq 3x$ ULN
Blood urea nitrogen (BUN)	≥ 10.71 mmol/L
Creatinine	≥ 177 μ mol/L
Uric acid	≥ 625 μ mol/L
Men	
Women	≥ 506 μ mol/L
Bilirubin (total)	$\geq 2x$ ULN
Potassium	≤ 3 mmol/L ≥ 6 mmol/L
Calcium	≤ 1.5 mmol/L ≥ 3.5 mmol/L
Hematology	
Hemoglobin	≤ 115 g/L
Men	
Women	≤ 95 g/L
White blood cell (WBC) counts	$\leq 3 \times 10^9$ /L $\geq 20 \times 10^9$ /L
Absolute neutrophil counts (ANC)	$\leq 1 \times 10^9$ /L
Platelet counts	$\leq 75 \times 10^9$ /L $\geq 700 \times 10^9$ /L

ULN=upper limit of normal range.

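### Glucose and triglyceride changes from a normally fasting baseline are tabulated at visits where fasting is not required, chiefly V14, V17 and V20 in integrated tables without a placebo control

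*SAP*

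**What the plan says.** **Fasting.** The laboratory footnote to Protocol Table 1 reads: "Patients must fast for at least 8 hours prior to baseline (visit 2; week 0), visit 11 (week 8), and the EOT visit". The corresponding footnote to Table 2, covering Period 2, reads: "Patients must fast for at least 8 hours prior to visit 11 (week 8) and the EOT visit". Both add that fasting is preferable at the ET visit, and Protocol 6.6.2 repeats the Table 1 rule. V3, V7, V14, V17, V20 and the follow-up visit (FU) are not named.

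**Panel.** Protocol Table 9 lists glucose, "Total cholesterol", LDL, HDL and triglycerides under serum chemistry. Its footnotes limit prolactin, HbA1c and coagulation to certain visits but place no such limit on glucose or lipids.

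**Analysis.** SAP 8.6 reads: "Laboratory values and changes from baseline to each scheduled visit will be summarized using descriptive statistics". It applies the same scheme to shifts below, within and above the normal range, and adds an any-visit shift category. The readable SAP text does not mention fasting.

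**Baseline and control.** Under SAP 4.2, baseline is the last value before the first dose. For placebo patients in the integrated tables it is the Period 2 baseline, normally taken at V11. SAP 8.1 leaves placebo patients' Period 1 data out of the integrated summaries.

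**The concern.** A change from baseline can be read as a drug effect only if both samples were taken under like conditions. Here the baseline is normally fasting, while most later samples carry no fasting requirement. If some patients have eaten before those draws, the mean change contains a meal effect as well as any effect of treatment.

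This matters more for olanzapine than for most drugs. Protocol 2.3.1 cites label warnings on raised glucose, diabetes, weight and lipids. SAP Table 2 sets no potentially-clinically-significant limit for glucose or lipids, so in the readable plan the laboratory display of these analytes rests on the change and shift tables. The protocol draws the distinction itself in an exclusion criterion: "The patient has a non-fasting glucose level of ≥200 mg/dL at screening".

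The any-visit shift is the least forgiving summary. One high value after a meal moves a patient with a normal fasting baseline into the above-range category, and later fasting values cannot move that patient back.

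**Working it through.** The plan states no figure on this point, so there is none to reproduce. The check is a visit count followed by a simple bias calculation.

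**1. Visits with chemistry** (Protocol Tables 1 and 2, Appendix B; V20 repeats V14). Under SAP 4.4 the by-visit tables show scheduled visits, EOT and FU, but not ET.

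| Visit | Fasting required? |
|---|---|
| V3 (day 2) | No |
| V7 (week 4) | No |
| V11 (week 8) | Yes |
| V14 (week 20) | No |
| V17 (week 32) | No |
| V20 (week 44) | No |
| EOT | Yes |
| FU | No |

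- All post-baseline visits: not required at 6 of 8, or 75%.
- Leaving out FU: 5 of 7.
- Period 1 (V3, V7, V11): 2 of 3.
- Period 2 on treatment after V11 (V14, V17, V20, EOT): 3 of 4.

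**2. Bias within an arm.** Let f be the share of patients not fasting at a visit and d the mean fed-minus-fasted difference. With a fasting baseline, the arm's mean change shifts by f × d. The documents give neither quantity, so the ranges below are assumptions, for glucose only:

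- f = 0.25, d = 0.5 mmol/L: 0.25 × 0.5 = 0.125 mmol/L.
- f = 0.5, d = 1 mmol/L: 0.5 × 1 = 0.5 mmol/L.
- f = 1, d = 2 mmol/L: 1 × 2 = 2.0 mmol/L.

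**3. Bias between arms.** The active-minus-placebo difference shifts by (f_active − f_placebo) × d. With equal f the shift is 0. If f differs by 10 percentage points, it is 0.1 × 0.5 = 0.05 to 0.1 × 2 = 0.2 mmol/L.

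**4. Where each case applies.** The Period 1 tables have a randomised placebo column under the same fasting rule, so step 3 governs V3 and V7. The integrated tables have no placebo column, so step 2 governs V14, V17 and V20.

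**5. Any-visit shifts.** Under SAP 4.4 these use all visits, including unscheduled ones, so they pool samples with and without required fasting.

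**6. ET results.** SAP 4.4 also maps an ET result to a scheduled visit when it falls in that window and the scheduled result is missing. Fasting at ET is only preferred, so even the V11 column may contain some such values.

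**The case against.** The strongest reply is that the problem is narrow, and much of that reply stands.

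- **Not required does not mean not fasting.** A reader might infer that six of eight visits are non-fasting. The documents say only where fasting is compulsory; some patients may fast elsewhere.
- **The main time points are sound.** At V11 and EOT the change is normally fasting to fasting. Placebo roll-overs also start from V11.
- **Period 1 has a control.** V3 and V7 share their conditions with placebo. FU is summarised as a separate period under SAP 8.1 and 8.6. That leaves mainly V14, V17 and V20, and even there the dose groups follow one schedule, so comparisons between doses are not obviously distorted.
- **HbA1c covers glycaemia.** It is taken at V2, V11, V14, V17, V20 and EOT and does not depend on fasting. It says nothing about triglycerides.
- **Nothing is tested.** The tables are descriptive, and the potentially-clinically-significant counts are unaffected because SAP Table 2 has no glucose or lipid limits.
- **Dropping every lipid change table at six visits would go too far.** It would discard the usable placebo comparison at V7, and the argument here does not extend clearly to the cholesterol fractions.

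These points reduce the scope. They do not answer the within-arm changes at V14, V17 and V20, or the any-visit shifts. SAP 4.3.2 is blacked out, so a fasting rule there cannot be excluded, but its title concerns imputation of safety data and the governing text in 8.6 is readable.

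**Conclusion.** The concern holds in limited form. As written, SAP 8.6 compares samples taken without a fasting requirement with a normally fasting baseline. The exposed results are mainly glucose and triglyceride within-arm changes and shifts at V14, V17 and V20 in the integrated tables, plus the any-visit shifts.

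The size is unknown. The range of 0.125 to 2.0 mmol/L for glucose rests wholly on assumed values of f and d, and no comparable range is offered for triglycerides. The expected upward direction assumes that glucose and triglycerides are higher after food.

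A reader might go further and expect the long-term tables to show a mid-study rise that resolves at EOT because of fasting status alone. The visit pattern makes that possible, but the documents do not show it will happen, since actual fasting behaviour is not given. Nor do they support a claim that the Period 1 comparison with placebo is materially biased: under equal fasting behaviour the shift is zero. This is a cheap improvement to a safety display tied to a labelled risk. It has no bearing on the efficacy conclusions.

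**What to change.** In SAP 8.6, for glucose and triglycerides (other lipids optional):

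1. Base the main change-from-baseline, shift and any-visit shift tables on V11 and EOT only, or on samples with recorded fasting status if that was captured.
2. Show V3, V7, V14, V17, V20 and FU in a separate table labelled *fasting not required*, so that no data are lost.
3. Flag ET results that are mapped to a scheduled visit.

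The cost is one SAP paragraph, one additional table and fewer time points in the main change tables: 2 of 8 if the visit rule is used. HbA1c stays as planned. No new data collection or protocol change is needed. SAP 2.6.2 places the final safety analysis after study completion and provides for later changes to be disclosed in the clinical study report, so the integrated tables can still be specified this way.

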- ALT or AST $>3 \times$ ULN, and in addition either total bilirubin level $>2 \times$ ULN or international normalized ratio >1.5 (if elevation of international normalized ratio is not caused by anticoagulants)
- ALT or AST $>3 \times$ ULN with the appearance of fatigue, nausea, vomiting, right upper quadrant pain or tenderness, fever, rash, and/or eosinophilia ($>5\%$)
 - x. The patient has a neutrophil count of $<1200/\text{mm}^3$.
 - y. The patient has platelet count $\leq 75 \times 10^3 \mu\text{L}$.
 - z. The patient has serum creatinine $>2.5 \text{ mg/dL}$.
- aa. The patient has a positive serology for human immunodeficiency virus (HIV)-1, HIV-2, hepatitis B surface antigen, and/or hepatitis C. If serology is positive for hepatitis C but the ribonucleic acid (RNA) test is negative, and the patient has no history of liver disease or symptoms of active liver disease, enrollment will be allowed based on clinical judgment.
- bb. The patient is a pregnant or lactating woman or plans to become pregnant during the study.
- cc. The patient has previously participated in this study (except for rescreening).
- dd. The patient is or has been using or consuming the medications prohibited in this protocol.
- ee. The patient used an investigational drug (new chemical entity) or a medical device in a clinical study within 30 days or 5 half-lives (whichever is longer), or, in case of a biologic investigational drug, within 3 months or 5 half-lives (whichever is longer) prior to the first TV-44749 administration.
- ff. The patient has donated or received any blood, plasma, or platelet transfusions within 30 days prior to the study or have planned donations during the study period or 6 months following the last dose of IMP administration.
- gg. The patient has a pending court appearance that may result in incarceration.

5.3. Eligibility Criteria for Period 2

In order to enter Period 2, the patient should meet the following eligibility criteria:

1. Patient has completed Period 1.
2. Patient is considered sufficiently clinically stable per the investigator's judgment.
3. Patient is an outpatient (ie, met RDQ criteria and was discharged prior to Period 2).

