4.4. Study Days and Visits

Study days will be numbered relative to the first day of IMP administration (i.e., the first administration in Period 1). The start of treatment (Day 1) is defined as the date for which a patient receives the first dose of study drug, as recorded on the Case Report Form (CRF). Days will be numbered relative to treatment start (i.e., ..., -2, -1, 1, 2, ...; with Day 1 being the first day of study drug administration and day -1 being the day before the first day of study drug administration).

In case the Early Termination (ET)/End-of-Treatment (EOT) visit occurred on the allowed time window for any scheduled visit (according to Table 1 and Table 2 of the study protocol), and the scheduled visit results are missing, the results from the overlapping ET/EOT visit will be mapped to the scheduled visit.

In case the EOT or Follow-up visit assessments were collected out of the allowed time window, assessment results will be excluded from the by-visit summary tables but will be included in relevant listings. In addition, if there are multiple assessments at a post-baseline visit day, then the last non-missing assessment at that visit will be used, unless otherwise specified.

For the by-visit summary tables, only scheduled visits, EOT and follow-up visits will be presented. The ET visit will not be presented, and unscheduled visits will not be mapped or presented. For the 'at any time' summary statistics in the shift tables and in the presentation of Potentially Clinically Significant (PCS) summaries, all visits will be used (including unscheduled visits).

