8. SAFETY ANALYSIS

8.1. General

Safety analyses will follow the safety estimand approach using the safety analysis sets.

Safety will be assessed by qualified study personnel by evaluating reported adverse events (including serious adverse events, extrapyramidal symptoms, injection pain, injection site findings and Injection Site Reactions [ISRs]), vital signs (blood pressure, pulse and orthostatic changes, and temperature), body weight and BMI, laboratory tests, ECG, concomitant medication use, time to all-cause discontinuation, all-cause discontinuation rates and discontinuation rates due to adverse events (tolerability), time to all discontinuation by reason, and safety rating scales (including Abnormal Involuntary Movement Scale [AIMS], Barnes Akathisia Rating Scale [BARS], Simpson-Angus Scale [SAS], C-SSRS, and CDSS).

Safety assessments and time points are provided in Table 1 (for Period 1) and Table 2 (for Period 2) of the study protocol.

The safety analysis will be performed separately for Period 1 and for the integrated study periods.

The safety analysis for Period 1 will be performed by treatment group and overall (total).

The safety analysis for the integrated study periods that will be presented in the CSR and in the IDMC closed reviews, will be performed by treatment group. Specifically, for IDMC closed reviews, patients rolling over from Placebo group will be distinguished from patients who continued their active treatment assignment from Period 1. Data from Period 1 for placebo patients will not be included in the integrated summaries.

For the open sessions of the IDMC reviews, data from Period 1 and from Period 2 will be presented separately. Summary tables will be generated for each period and will only be presented as a single total column.

For the following safety variables: Adverse events, Clinical laboratory results, ECG, weight and BMI and Vital signs, a separate safety summary will be presented for the 'While on Treatment' period, defined as the period between the first IMP administration visit until and including the End of Treatment visit (including the Early Termination visit if conducted during this period). In addition a separate safety summary table and listing will be presented for the Follow-Up period, defined as the period after the End of Treatment/Early Termination visit until the end of the study.

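### SAP 8.6 counts potentially clinically significant laboratory values without regard to baseline, although entry criteria admit patients already over some of the limits

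*SAP*

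**What the plan says.** **Counting rule.** SAP 8.6 states: "Summaries of potentially clinically significant abnormal values will include all post-baseline values (including scheduled, unscheduled, and withdrawal visits". The result is labelled an incidence: "The incidence of potentially clinically significant abnormal values will be summarized for laboratory variables using descriptive statistics with the criteria specified in" Table 2. SAP 4.4 widens the net in the same direction: "in the presentation of Potentially Clinically Significant (PCS) summaries, all visits will be used (including unscheduled visits". Neither section asks whether the patient already met the limit before dosing, or whether the value got worse.

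**PCS limits (SAP Table 2).** ALT is flagged as "Alanine aminotransferase (ALT) $\geq 3x$ ULN", with the same limit for AST. Total bilirubin is flagged from 2 x ULN and creatinine from 177 µmol/L. Hemoglobin, WBC, BUN, uric acid and several other analytes also have limits.

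**Entry limits (Protocol 5.2).** Criterion w first requires raised ALT, raised AST and raised bilirubin together. It then adds a list headed "Isolated parameters for exclusion are as follows", whose first entry is "ALT or AST $>5 \times$ ULN". The other two entries exclude ALT or AST above 3 x ULN only with raised bilirubin or INR, or with named symptoms or eosinophilia. Criterion z ("The patient has serum creatinine") excludes only above 2.5 mg/dL.

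**Integrated tables.** SAP 8.1 states: "Data from Period 1 for placebo patients will not be included in the integrated summaries".

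**The concern.** A reader takes an incidence under a treatment column to mean abnormalities that arose on that treatment. Here the column can also contain abnormalities the patient brought into the trial. Safety is a stated secondary objective, and the integrated PCS tables have no placebo column against which to judge that background.

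The SAP does condition on baseline elsewhere. The prolactin PCS summary in 8.6.2.4 counts moves from normal to 2 x and 5 x ULN, and adverse events are summarized as treatment-emergent in 8.4. The Table 2 analytes have no equivalent rule. The laboratory shift tables do not supply one, because they use the normal range and not the PCS limit. A patient at 4 x ULN throughout and a patient rising from 1.1 x to 10 x ULN both appear as above-to-above.

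**Working it through.** The plan gives no figure to reproduce. The check compares each entry limit with its PCS limit, then shows what the counting rule does to a percentage.

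**Step 1. Do the limits overlap?** Creatinine needs a unit conversion that the documents do not give. The standard factor is assumed: 1 mg/dL = 88.42 µmol/L. Then 177 / 88.42 = 2.00 mg/dL and 2.5 x 88.42 = 221 µmol/L.

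| Analyte | Excluded at entry (Protocol 5.2) | PCS (SAP Table 2) | Both eligible by number and PCS |
|---|---|---|---|
| ALT or AST, isolated, no symptoms | >5 x ULN | ≥3 x ULN | 3 to 5 x ULN |
| Creatinine | >2.5 mg/dL (221 µmol/L) | ≥177 µmol/L | 177 to 221 µmol/L |
| Total bilirubin, isolated | no numeric limit | ≥2 x ULN | ≥2 x ULN |
| Hemoglobin, WBC, BUN, uric acid | no numeric limit | limits given | any value over the PCS limit |
| Neutrophils | <1200/mm³ = 1.2 x 10⁹/L | ≤1 x 10⁹/L | none |
| Platelets, low | ≤75 x 10³/µL = 75 x 10⁹/L | ≤75 x 10⁹/L | none |

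Alkaline phosphatase, LDH, potassium, calcium and high platelets likewise have a PCS limit and no numeric entry limit.

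**Step 2. When is an entry abnormality counted?** Only when a post-baseline value also meets the limit, so it must persist or recur. One seen only before dosing is not counted.

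**Step 3. Size in one column.** Let b be the share of patients over the limit at baseline, q the share of those still or again over it later, and i the new incidence among patients not over it at baseline. The reported percentage is

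crude = b·q + (1 − b)·i.

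The documents give none of b, q or i, so all are assumptions. Take i = 1% and the planned Period 1 arm size of 640 / 4 = 160.

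| b | q | crude | patients of 160 | share carried over, b·q / crude |
|---|---|---|---|---|
| 0.5% | 0.5 | 0.25% + 0.995% = 1.25% | 2.0 | 20% |
| 1% | 1 | 1% + 0.99% = 1.99% | 3.2 | 50% |
| 2% | 1 | 2% + 0.98% = 2.98% | 4.8 | 67% |
| 5% | 1 | 5% + 0.95% = 5.95% | 9.5 | 84% |

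If incidence is restricted to patients not over the limit at baseline, every row reads 1%.

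**Step 4. Period 1 comparison with placebo.** Randomization makes b equal across arms in expectation. If q is also equal, the difference in crude percentages is (1 − b)(i_active − i_placebo). With i = 1% on drug, 0.5% on placebo, b = 2% and q = 1, the table shows 2.98% against 2.49%. The difference is 0.49 points, where the new incidences differ by 0.50. At b = 5% the difference is 0.95 x 0.5 = 0.475 points. The ratio shrinks from 2.0 to 2.98 / 2.49 = 1.20 at b = 2%, but no such ratio is planned.

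**Step 5. Integrated tables.** Placebo patients' Period 1 data are left out, so the b·q term falls wholly in TV-44749 columns. For placebo patients who roll over, SAP 4.2 resets baseline to the last value before the third injection. An entry abnormality still present after that point is then counted under their Period 2 dose.

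**The case against.** The strongest reply is that this is a small gap in a descriptive table.

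- **Eligibility is not purely numeric.** Inclusion p asks for adequate health on laboratory and other grounds, exclusion p removes clinically significant uncontrolled conditions, and exclusion n removes conditions that could endanger the patient. This stands in part: these criteria narrow the group admitted, but they rest on judgement and set no number at the PCS limits.
- **Liver and marrow signals have other routes.** Hy's law cases are serious adverse events and are listed separately (SAP 8.6.1). Laboratory results judged clinically significant become adverse events (Protocol 8.4), defined as findings that develop or worsen. Neutrophils and low platelets do not overlap. A reader might infer that the counting rule would hide a hepatic or hematologic signal. The documents do not support that.
- **No ratio to placebo is planned.** PCS results are descriptive, and Step 4 shows that the Period 1 difference is essentially unchanged. A reader might infer that the placebo comparison is biased. It is not, in expectation.
- **Other outputs help.** Changes from baseline, shift tables and full listings let a reader trace individual cases. They do not correct the PCS percentage.
- **Counting all values is the more inclusive convention.** Simply dropping patients over the limit at baseline would lose someone who enters at 3.5 x ULN and rises to 8 x ULN on drug. This stands, and it shapes the fix.

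**Conclusion.** The point holds as a gap in the counting rule. SAP 8.6 calls a count incidence without reference to baseline, the numeric entry criteria admit patients already over some of the limits, and no other section corrects the count. In Period 1 the effect is a roughly equal inflation of all arms in expectation. In the integrated columns it is attributed to TV-44749, and that is where it matters most.

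The size is unknown. The percentages in the working rest wholly on assumed b, q and i. A reader might infer from the 2% row a threefold overstatement (2.98% against 1%). That needs 2% of patients over one limit at entry, all remaining over it, and a new incidence of only 1%; the mildest case shown is 1.25% against 1%. Nor is every entry abnormality counted, only those that persist or recur. The primary and key secondary efficacy analyses are untouched, and nothing here bears on which entry limit is right. This is a cheap improvement.

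**What to change.** In SAP 8.6, tabulate PCS values by PCS status at the baseline that SAP 4.2 defines for the summary in question, including the reset baseline for placebo patients in the integrated tables:

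1. Incidence: patients with a post-baseline value meeting the Table 2 criterion, among those who did not meet it at baseline and have at least one post-baseline value.
2. A separate line: patients who met the criterion at baseline, and how many of them worsened post-baseline. The SAP should state in advance what counts as worsening.
3. Keep all values in the listings, so that nothing is lost.

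The cost is a few sentences of SAP text, a programming condition, slightly smaller denominators per parameter and one extra table row. No eligibility rule or study procedure changes.
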